4.2. Scientific Rationale for Study Design

The single-arm, open-label design is appropriate for a Phase 2 study to evaluate the clinical benefit of adjuvant apalutamide with ADT for patients with high-risk localized prostate cancer following RP. The occurrence of rash with apalutamide and subsequent specific management could make blinding impractical. The participants have previously selected to undergo RP as opposed to any other option and their participation in this study with adjuvant treatment could provide added benefit to them.

Following the work conducted by the ICECaP investigators²⁹ whose results were obtained mostly in patients who had undergone radiation therapy with curative intent, Martini et al¹⁴ described the biochemical and clinical recurrence patterns in a cohort of 3,507 patients with high risk localized prostate cancer who had undergone RP and extended pelvic lymph node dissections. These investigators noted negligible serum PSA (≤ 0.2 ng/mL) rates of 84% and 76% at 12 and 24 months, respectively after surgery, in the absence of any adjuvant treatment. These findings on biochemical recurrence form the basis for the statistical assumptions and rationale for clinical endpoints in this adjuvant study (see Section 9.2).

Biomarker Collection

It is recognized that genetic variation can be an important contributory factor to interindividual differences in intervention and response and can also serve as a marker for disease susceptibility and prognosis.

Biomarker samples may be collected to evaluate progression or help to explain interindividual variability in clinical outcomes and may help to identify population subgroups that respond differently to this intervention. The goal of the biomarker analyses is to evaluate localized high-risk prostate cancer population and aid in evaluating the intervention-clinical response relationship of apalutamide with ADT.

Biomarker samples may be used to help address emerging issues and to enable the development of safer, more effective, and ultimately individualized therapies.

4.2.1. Participant Input Into Design

As part of the Patient Voice Project, members of the Prostate Cancer Patient Engagement Research Council who are all patients/survivors of prostate cancer favorably reviewed the study design and visit schedule.

The consensus was that the open-label design, without placebo, of this study is preferable to randomized double-blind studies for patients. Additionally, the visit schedule and duration of time on study was not considered "burdensome". Longer follow-up was suggested and follow-up every 6 months until the end of the study was added with subsequent follow-up to be covered by treatment per standard of care.

4.2.2. Study-Specific Ethical Design Considerations

Potential participants will be fully informed of the risks and requirements of the study and, during the study, participants will be given any new information that may affect their decision to continue participation. They will be told that their consent to participate in the study is voluntary and may be withdrawn at any time with no reason given and without penalty or loss of benefits to which they would otherwise be entitled. Only participants who are fully able to understand the risks, benefits, and potential AEs of the study, and provide their consent voluntarily will be enrolled.

While participants have selected RP independent from this study, the primary ethical concern is that adjuvant therapy with apalutamide following RP is not currently standard of care. The cure rate for patients with high-risk localized prostate cancer is approximately 25%. Apalutamide has been proved to significantly delay metastases and improve overall survival, and has a manageable safety profile.²⁵ Participants may discontinue from the study if there are signs of disease progression and then be eligible for other forms of treatment including radiation.

An additional ethical concern is germline and other genetic testing which may warrant counselling. This information and potential interventions may affect not only the participant, but his family. Genetic counselling will be made available through the genetic testing facility.

The total blood volume to be collected is considered to be an acceptable amount of blood to be collected over this time period from the population in this study based upon the standard of the American Red Cross.¹

4.3. Justification for Dose

The dose of 240 mg (4 \times 60 mg tablets) is the approved dose per ERLEADA USPI.

4.4. End of Study Definition

End of Study Definition

The EOS is defined as the date of last participant's enrollment +24 months or discontinuation of all study participants from the study, whichever occurs first. The final data from the study site will be sent to the sponsor (or designee) after completion of the final participant visit at that study site, in the time frame specified in the Clinical Trial Agreement.

Study Completion Definition

Participants will be considered to have completed the study if they have completed EOS assessments.

Participants who prematurely discontinue study intervention for any reason before study completion will not be considered to have completed the study. If a participant misses a dose for >28 days, consult the sponsor regarding continuation in the study.

5. STUDY POPULATION

The study population will consist of participants that are treatment-naïve, who have undergone RP for non-metastatic prostate cancer, and who are at high risk for metastases, as defined by Gleason score or PSA.

Screening for eligible participants will be performed within 90 days before administration of the study intervention. Refer to Section 5.4, Screen Failures for conditions under which the repeat of any screening procedures are allowed.

The inclusion and exclusion criteria for enrolling participants in this study are described below. If there is a question about these criteria, the investigator must consult with the appropriate sponsor representative and resolve any issues before enrolling a participant in the study. Waivers are not allowed.

For a discussion of the statistical considerations of participant selection, refer to Section 9.2, Sample Size Determination.

5.1. Inclusion Criteria

Each potential participant must satisfy all of the following criteria to be enrolled in the study:

- 1. male ≥ 18 years of age
- 2. must be willing and able to sign an informed consent form and be able to fully comply with all of the required procedures, restrictions, and prohibitions specified in this protocol
- 3. Criterion modified per Amendment 2
 - 3.1 The participant should be
 - a. a candidate for RP or status post-RP
 - b. eligible to receive study intervention between Day 29 and Day 90 post-RP
 - c. post-RP PSA of ≤ 0.2 ng/mL
 - d. has not received other treatment for prostate cancer

4. Criterion modified per Amendment 2

4.1 have recovered from RP procedure and have had no worsening in cardiac risk in the peri-operative period per the clinical judgment of the investigator

5. Criterion modified per Amendment 1

5.1. Criterion modified per Amendment 2

5.2 histologically confirmed adenocarcinoma of the prostate and categorized as high risk for recurrent prostate cancer. High risk can be defined based on PSA alone or biopsy or RP specimen as follows:

- $PSA \ge 20 \text{ ng/mL}$

or

- Gleason Score ≥ 9 in any core on biopsy

or

- Gleason Score ≥ 8 (4+4 or 5+3) in $\geq 80\%$ of 2 cores on biopsy

or

 Gleason Score = 8 (4+4 or 5+3) in 1 core as long 5 or more other cores with minimum Gleason Score of 4+3 on biopsy

The determination of high risk may be based on pathology report of biopsy or equivalent criteria from radical prostatectomy.

- 6. adequate organ function (hepatic, renal, hematologic and cerebral) determined at the discretion of the treating physician
- 7. Eastern Cooperative oncology Group (ECOG) Performance Status Score of 0 or 1
- 8. able to take apalutamide per the ERLEADA USPI and able to receive ADT for up to 1 year
- 9. must be willing to wear a condom when engaging in any activity that allows for passage of ejaculate to another person. Male participants should also be advised of the benefit for a female partner to use a highly effective method of contraception as condom may break or leak
- 10. must be willing to agree not to donate sperm for the purpose of reproduction during the study and for a minimum 90 days after receiving the last dose of study intervention

5.2. Exclusion Criteria

Any potential participant who meets any of the following criteria will be excluded from participating in the study:

1. Criterion modified per Amendment 1

1.1. history or presence of soft tissue/bone metastasis or metastasis in distant lymph nodes (pelvic lymph nodes below the iliac bifurcation that are <2 cm in diameter [short axis] either radiographically or pathologically are allowed.)

- 2. history of bilateral orchiectomy
- 3. taking any disallowed therapies or chronic need for prohibited medications (per ERLEADA USPI) as noted in Section 6.8, Concomitant Therapy before the planned first dose of study intervention
- 4. received an investigational intervention ≤4 weeks before the planned first dose of study intervention
- 5. history of seizure or any condition that in the opinion of the investigator may predispose to seizure or treatment with drugs known to lower the seizure threshold within 4 weeks prior to starting treatment with apalutamide
- 6. allergy or hypersensitivity to apalutamide, or excipients, unable or unwilling to take ADT
- 7. history or presence of psoriasis, neurodermatitis, acneiform rashes or any dermatological condition that in the opinion of the investigator may predispose to confounding with the evaluation and management of study intervention related rash
- 8. Criterion modified per Amendment 2

8.1 malignancies (ie, progressing or requiring treatment or treatment change in the last 24 months) other than prostate cancer. The only allowed exceptions are: non-muscle invasive bladder cancer; skin cancer (non-melanoma or melanoma) treated within the last 24 months that is considered completely cured. Malignancies considered cured for more than 24 months are allowed

9. Criterion modified per Amendment 1

9.1 Criteria modified per Amendment 2

9.2 any of the following within 12 months prior to baseline: severe or unstable angina, myocardial infarction, symptomatic congestive heart failure, uncontrolled hypertension, long QT, arterial or venous thromboembolic events (eg, pulmonary

embolism, cerebrovascular accident including transient ischemic attacks), or clinically significant ventricular arrhythmias

- 10. plans to father a child while enrolled in this study or within 12 weeks after the last dose of study intervention
- 11. any condition for which, in the opinion of the investigator, participation would not be in the best interest of the participant (eg, compromise the well-being) or that could prevent, limit, or confound the protocol-specified assessments

NOTE: Investigators should ensure that all study enrollment criteria have been met at screening. If a participant's clinical status changes (including any available laboratory results or receipt of additional medical records) after screening but before the first dose of study intervention is given such that the participant no longer meets all eligibility criteria, then the participant should be excluded from participation in the study. The required source documentation to support meeting the enrollment criteria are noted in Section 10.3, Appendix 3, Regulatory, Ethical, and Study Oversight Considerations.

5.3. Lifestyle Considerations

Potential participants must be willing and able to adhere to the following lifestyle restrictions during the course of the study to be eligible for participation:

- 1. Refer to Section 6.8, Concomitant Therapy for details regarding prohibited and restricted therapy during the study, including chronic alcohol use, cytochrome P450 (CYP)3A4 interaction, and drugs known to lower the seizure threshold or cause seizures.
- 2. Agree to follow all requirements that must be met during the study as noted in the Inclusion and Exclusion Criteria (eg, contraceptive requirements).
- 3. Orchiectomy is prohibited during the entire study.
- 4. A condom is required for all sexual activity during the study and for 3 months after completion of apalutamide. There is no sperm donation permitted during the study and within 3 months after completion of study treatment. See Section 10.5, Appendix 5, Contraceptive Guidance for further details.
- 5. If the study participant is engaged in sexual activity with a female of childbearing potential, 2 forms of contraception, including condom use as described above, are required. These include:
 - Oral, injected or implanted methods of contraception including an intrauterine device (IUD) or intrauterine system (IUS)
 - Barrier methods with spermicide

• Vasectomy

5.4. Screening Failures

Participant Identification, Enrollment, and Screening Logs

The investigator agrees to complete a participant identification and enrollment log to permit easy identification of each participant during and after the study. This document will be reviewed by the sponsor study-site contact for completeness.

The participant identification and enrollment log will be treated as confidential and will be filed by the investigator in the study file. To ensure participant confidentiality, no copy will be made. All reports and communications relating to the study will identify participants by participant identification and age at initial informed consent. In cases where the participant is not enrolled into the study, the date seen and age at initial informed consent will be used.

Participants who do not meet the criteria for participation in this study (screen failure) will not be rescreened.

5.5. Criteria for Temporary Delaying (Enrolment/Randomization/Administration of Study Intervention) (Not Applicable)

6. STUDY INTERVENTION

6.1. Study Intervention Administered

The study intervention apalutamide, 240 mg (four 60 mg tablets, slightly yellowish to greyish green oblong film-coated tablets, debossed with "AR 60" on one side), will be provided as tablets for oral administration. The window for initiation of study intervention must occur between Day 29 and Day 90 post-RP. Participants will be instructed to take their assigned dose of the study intervention orally **once daily** for 12 cycles per ERLEADA USPI. A treatment cycle is defined as 28 days. Apalutamide can be taken with or without food. If a participant experiences a \geq Grade 3 toxicity or an intolerable side effect, hold dosing until symptoms improve to \leq Grade 1 or original grade, then resume at the same dose or a reduced dose (180 mg or 120 mg), if warranted. If a participant remains off apalutamide for \geq 4 weeks, the participant may be withdrawn from the study, after discussing with the sponsor. Participants experiencing treatment related seizure of any grade will have apalutamide permanently discontinued.

Description of Interventions

Study intervention administration must be captured in the source documents and the electronic case report form (eCRF). Study-site personnel will instruct participants on how to store study intervention for at-home use as indicated for this protocol.

Apalutamide will be manufactured and provided under the responsibility of the sponsor. Refer to the IB for a list of excipients and the ERLEADA USPI.

Investigator's choice of a Food and Drug Administration (FDA)-approved and commercially available ADT, not provided by the sponsor, will be administered per the USPI for 12 months in total duration, during the treatment phase. Three-month depot is the preferred administration. For further information on ADT refer to the USPI.

For a definition of study intervention overdose, refer to Section 6.7, Treatment of Overdose.

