7. DISCONTINUATION OF STUDY INTERVENTION AND PARTICIPANT DISCONTINUATION/WITHDRAWAL

7.1. Discontinuation of Study Intervention

A participant's study intervention must be discontinued if:

- The participant withdraws consent to receive study intervention
- The investigator believes that for safety reasons or tolerability reasons (eg, AE) it is in the best interest of the participant to discontinue study intervention
- Noncompliance with study intervention administration
- Participants experiencing treatment-related seizure of any grade will have apalutamide permanently discontinued

If a participant discontinues study intervention for any reason before the end of the study, then the last scheduled study assessments should be obtained and scheduled assessments off study intervention should be continued. If a participant misses doses for >28 days, consult the sponsor regarding continuation in the study. If a participant discontinues study intervention due to disease progression, the subsequent treatment including radiation will be captured in the eCRF, if known. Additional participants will not be entered to ensure the protocol-specified number of participants complete the study.

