7.2. Participant Discontinuation/Withdrawal From the Study

A participant will be withdrawn from the study for any of the following reasons:

- Lost to follow-up
- Withdrawal of consent

- Investigator's discretion
- Seizure
- Death

When a participant withdraws before study completion, the reason for withdrawal is to be documented in the eCRF and in the source document. If the reason for withdrawal from the study is withdrawal of consent, then no additional assessments are allowed.

Withdrawal of Consent

A participant declining to return for scheduled visits does not necessarily constitute withdrawal of consent. Alternate follow-up mechanisms that the participant agreed to when signing the consent form apply (eg, consult with family members, contacting the participant's other physicians, medical records, database searches, use of locator agencies at study completion) as local regulations permit.

Prior to a participant withdrawing consent for follow-up, the investigator should offer the participant an opportunity for one of the alternative reduced follow-up mechanisms described below. Withdrawal of consent should be an infrequent occurrence in clinical studies, therefore, prior to the start of the study, the sponsor and the investigator should discuss and reach a clear understanding of what constitutes withdrawal of consent in the context of the available reduced follow-up mechanisms listed.

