9.4.1. General Considerations

Primary endpoint test of hypothesis will be performed at 1-sided significant level 0.05; a 2-sided alpha level of 0.10 will be used to provide all confidence intervals.

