5.3.2. Estimand

The primary estimand, the main clinical quantity of interest to be estimated in the study, is defined by the following 4 components -

5.3.2.1. Population:

Subjects with high-risk localized or locally advanced prostate cancer who are treatment-naïve and have undergone RP for non-metastatic prostate cancer with post RP PSA ≤ 0.2 ng/mL

5.3.2.2. Variables:

• Time to confirmed BCR (confirmed PSA > 0.2 ng/mL).

5.3.2.3. Intercurrent Events and Strategies:

Table 1

| Intercurrent Events (IE) | Strategy for Addressing IE | Description of Strategy | Data to be Included |
|---|------------------------------------|---|--|
| Treatment discontinuation during treatment phase but continuing in the study. | Treatment Policy strategy | Occurrence of the IE is considered irrelevant in defining the treatment effect of interest | PSA value at the time of the primary analysis |
| Study withdrawal due to any reason, any time during the study (including treatment & study discontinuation during treatment phase) | While-on- Treatment strategy | Response to treatment prior to the occurrence of the IE is of interest | PSA value at the time of study withdrawal |
| Use of restricted and prohibited concomitant therapy any time during the study | While-on- Treatment strategy | Response to treatment prior to the occurrence of the IE is of interest | PSA value at the time of the start of restricted and prohibited concomitant therapy |
| Other protocol deviations | Treatment Policy strategy | Occurrence of the IE is considered irrelevant in defining the treatment effect of interest | PSA value at the time of the primary analysis |
| Death | While-Alive strategy | Response to treatment prior to the occurrence of the IE is of interest | PSA value at the time of death |

5.3.2.4. Population level summary:

Time to confirmed BCR endpoint: Kaplan-Meier method will be used to estimate BCR-free rate at primary time point (24 months) along with 95% confidence interval.

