5.3.3. Analysis Methods

The analysis of time to BCR will be performed at the end of study which is defined as the date of last participant's enrolment + 24 months or discontinuation of all study participants from the study, whichever occurs first. The distribution of time to BCR will be estimated using the Kaplan-Meier (KM) method. Median BCR-free time along with 90% confidence interval will be reported with Kaplan-Meier curve. The null hypothesis will be rejected if lower limit of the 90% confidence interval of KM estimate of BCR-free rate at 24 months is > 76%.

Time to unconfirmed BCR will be evaluated using same methodology as sensitivity analysis.

Modified ITT analysis set will be used for the analysis. Subjects with no evidence of BCR will be censored based on following rule:

- If the subject does not have baseline PSA measurement, the subject will be censored on the date of enrollment (Study Day 1)
- If the subject does not have confirmed PSA >= 0.2 ng/mL, the subject will be censored on the date of the last PSA measurement
- If the subject receives a protocol specified prohibited or restricted therapy, PSA measurements on or after such therapy will not be included in the analysis

These censoring rules will be applied appropriately to all intercurrent events in the trial as defined in Table 1. The details are as specified in Table 2.

| Intercurrent Event (IE) / EOS | Censoring (if no event, before the IE) | Assumption |
|--|---|---|
| IE: Study withdrawal due to any reason, any time during the study | PSA value censored at study withdrawal | Non-informative censoring as per censoring rule |
| IE: Use of restricted and prohibited concomitant therapy any time during the study | PSA value censored at the last PSA assessment prior to the time of the start of restricted and prohibited concomitant therapy | Non-informative censoring as per censoring rule |

Table 2: Censoring Rules to be used for intercurrent events

| IE: Death | PSA value censored at the last PSA assessment prior to the time of death | Non-informative censoring as per censoring rule |
|--------------|--|---|
| End of study | (Administratively) censored at the last PSA assessment prior to the end of the study | Non-informative censoring as per censoring rule |

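### The protocol is inconsistent on whether men who stop apalutamide stay in follow-up; leavers are censored as non-informative and no analysis tests that assumption

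*Protocol*

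**What the plan says.** **Follow-up after stopping treatment.** Protocol 7.1 says that when a participant stops study intervention for any reason, "scheduled assessments off study intervention should be continued".

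**Routes out of the study.**
- Protocol 6.1: after four weeks or more off apalutamide, "the participant may be withdrawn from the study, after discussing with the sponsor". Sections 4.4 and 7.1 ask only for a sponsor consultation after more than 28 days of missed doses.
- Protocol 7.2: "A participant will be withdrawn from the study for any of the following reasons". The list includes seizure. Sections 6.1 and 7.1 make a treatment-related seizure a reason to stop apalutamide permanently and do not mention leaving the study.
- Protocol 4.2.2: "Participants may discontinue from the study if there are signs of disease progression", after which they may have other treatment, including radiation.

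**Handling in the analysis.** SAP 5.3.2, Table 1, applies treatment policy to "Treatment discontinuation during treatment phase but continuing in the study". A separate row covers study withdrawal for any reason, including men who stop treatment and leave together, under a While-on-Treatment strategy. SAP 5.3.3, Table 2, censors these men under the assumption "Non-informative censoring as per censoring rule". It uses the same assumption for restricted or prohibited therapy, death and end of study. The only named sensitivity analysis of the primary endpoint is time to unconfirmed BCR.

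**Censoring date.** SAP 5.3.1 censors men without an event at their last PSA in the treatment phase; 5.3.3 uses the last PSA measurement without that limit.

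**The concern.** Two similar men who stop apalutamide early can be handled in opposite ways. One stays, and every later PSA counts. The other is withdrawn and is censored. Which happens depends partly on site and sponsor judgement, in an open-label single-arm trial tested against a fixed 76%.

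Censoring is harmless if leavers have the same later risk of BCR as men who stay. That is doubtful for men who leave at signs of progression, and uncertain for men who have had less treatment. If leavers are at higher risk, the men who remain are a better-prognosis group and the 24-month rate comes out too high. Loss unrelated to risk costs power only, but the sample-size text states no dropout allowance and Protocol 7.1 rules out replacement.

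**Working it through.** **Inputs from the documents.** N = 94, null 76%, alternative 86%, exponential model (Protocol 9.2). "Primary endpoint test of hypothesis will be performed at 1-sided significant level 0.05" (Protocol 9.4.1). The null is rejected if the lower 90% limit of the Kaplan-Meier (KM) rate exceeds 76% (Protocol 9.4.2; SAP 5.3.3). The interval type is not named, so log-log and plain limits are both shown.

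**The plan's own figure.** An arcsine one-sample formula reproduces it:

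n = [(1.645 + 0.842) / (2(asin√0.86 − asin√0.76))]² = (2.487 / 0.257)² ≈ 93.6, so 94.

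This match does not come from the stated exponential model, and it contains no allowance for loss.

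**Assumptions not in the documents.** A share w of men leaves during months 3-12. Leavers' own 24-month BCR-free rate is a. The rate b for the others is set so that the true overall rate is exactly 76%: b = (0.76 − w·a)/(1 − w). For w = 10% and a = 60%, b = (0.76 − 0.06)/0.90 = 77.8%. This b is a ceiling on the bias, because leavers contribute some time and events before they go.

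**Simulated decision rule, true rate 76%.**

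| Share leaving | Leavers' own rate | b | Mean KM | Type I, log-log | Type I, plain |
|---|---|---|---|---|---|
| 0% | – | 76.0% | 76.0% | about 4% | about 7% |
| 2% | 60% / 50% | 76.3% / 76.5% | 76.2-76.3% | 4.6-5.1% | – |
| 5% | 60% / 50% | 76.8% / 77.4% | 76.5-76.9% | 5.7-6.0% | 8.7-10.4% |
| 10% | 60% / 50% | 77.8% / 78.9% | 77.3% / 78.1% | 6.8% / 9.9% | 11.0% / 15.4% |
| 20% | 60% / 50% | 80.0% / 82.5% | 78.9% / 80.5% | 13.3% / 20.7% | 18.8% / 29.8% |

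The 2% and 5% rows use continuous event times (6,000 runs). The 10% and 20% rows censor at the last PSA before withdrawal (3,000 runs).

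**Cross-check.** A second set-up (40,000 runs) has men leave over months 1-12, with a later hazard k times that of stayers. At w = 10% and k = 2 it gives KM 77.3% and type I 7.2% (log-log) / 11.5% (plain). The 10% / 60% cell implies a similar ratio: ln 0.60 / ln 0.778 ≈ 2.0. At k = 1 the mean KM is 76.0% for every w, so there is no bias.

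**Worked case.** With 22 true failures in 94, the rate is 1 − 22/94 = 76.6%. If m of the 22 leave early and are censored, KM ≈ 1 − (22 − m)/(94 − m).
- m = 5: 1 − 17/89 = 80.9%.
- m = 7: 1 − 15/87 = 82.8%. The plain lower limit is 0.828 − 1.645·√(0.828·0.172/87) ≈ 76.1%, so the null is rejected.
- m = 9: 1 − 13/85 = 84.7%. The log-log lower limit is about 76.9%; this is the first m at which the log-log rule rejects.

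**Power at a true 86%, loss unrelated to risk.** With 0%, 10% and 20% leaving: 77%, 73% and 69% (log-log); 85%, 81% and 78% (plain).

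**The case against.** **The estimand is respected.** A reader might infer that censoring leavers contradicts the SAP's treatment-policy strategy. It does not. Table 1 limits treatment policy to men who remain in the study, gives study withdrawal its own row, and Table 2 implements that row. What remains is that the protocol's exit wording decides which row a man falls in. KM under non-informative censoring also estimates the rate as if leavers had stayed, which fits the While-on-Treatment label poorly.

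**The exit routes are narrow.** Section 4.2.2 is ethics text, and progression is not on the 7.2 list. Section 6.1 is permissive and needs sponsor discussion. Men with a seizure history or predisposition are excluded, and nothing in the documents links seizure to BCR. Men off apalutamide may still be receiving ADT. All of this stands, and it argues for a small share of leavers.

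**Safeguards exist.** A confirmed BCR before leaving is an event, a raised PSA triggers confirmation outside the visit schedule, and the unconfirmed-BCR analysis counts a man who leaves after one value above 0.2 ng/mL. That also stands, but it misses a man who leaves with clinical signs or a rising PSA still at or below 0.2.

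**The completer wording looks like part of the problem.** Protocol 4.4 says "Participants who prematurely discontinue study intervention for any reason before study completion will not be considered to have completed the study". No censoring rule uses completion, so this affects only the disposition table and is not a source of bias.

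**Keeping men in the study is not enough.** A man who starts radiation before confirmed BCR is censored as having received prohibited therapy (Protocol Appendix 6; SAP 5.3.3) even if he attends every visit. That is correct, and the sensitivity analysis has to cover him.

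**Conclusion.** The inconsistency between Protocol 6.1, 7.1, 7.2 and 4.2.2 is real, and the non-informative assumption for leavers is untested. This is a cheap improvement, not a flaw that invalidates the primary analysis.

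The upward bias is conditional. With true rate 76% and leavers' own 24-month rate at 50-60%, it is about 0.2 to 0.9 points for 2-5% leaving, 1 to 2 points for 10% and 3 to 4.5 points for 20%. At 10%, type I error is about 7-10% (log-log) or 11-15% (plain), against about 4% and 7% with no leavers. If leaving is unrelated to risk there is no bias, only the power loss shown above. With plain limits, power still exceeds 80% at 10% loss.

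The documents give neither a withdrawal rate nor leavers' risk, so these are ranges under assumptions. They do not support a statement that the reported rate will be inflated.

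**What to change.** 1. **Protocol 6.1, 7.1, 7.2 and 4.2.2:** reconcile them, leaving treatment decisions unchanged, so that stopping treatment is separate from leaving the study. State that PSA and testosterone follow-up per the Schedule of Activities continues to end of study where the participant still consents. This review takes no position on which events should end treatment.
2. **SAP 5.3.3:** add one sensitivity analysis of the primary endpoint that counts as events, when they precede confirmed BCR, both study withdrawal for progression and the start of radiation or other subsequent prostate cancer therapy. The reason for withdrawal is already recorded (Protocol 7.2). Therapy after stopping for progression is captured only if known (7.1), so its completeness should be checked.
3. **SAP 5.3.1 and 5.3.3:** use one censoring date. Read literally, the treatment-phase limit in 5.3.1 would discard the off-treatment PSAs that the treatment-policy row needs; those values should be kept.

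Cost: wording changes in both documents, follow-up visits already in the schedule for a few men, and one extra analysis.
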